### 6.3.2. Open Label Phase

For purposes of the active open label phase, only active treatments will be applied with the Active therapeutic mode device parameters, as detailed above: stimulation waveform- symmetrical biphasic, phase duration 130-300 microseconds, pulse frequency 80Hz, trigeminal stimulation intensity – up to 6.7mA, Occipital stimulation intensity – up to 18mA.

The designated study central trainer will perform (on site or remote) the device conversion to the open label mode (i.e. conversion of the sham devices to active) with the subjects.

Open label phase treatment regimens would be as follows, according to the subject HDRS score at the end of the double-blind phase, for a period of 8±1 weeks:

**Maintenance treatment (for HDRS remitter subjects):** 40±10 minutes 3-4 times a week (intensity level up to 50).

**Daily treatment (for HDRS responder subjects):** 5-7 days a week (intensity level up to 50) 60±20 minutes per day (preferably in two equal sessions of 30±10 minutes each).

 Neurolief Brain Innovation	MOOD: CLINICAL INVESTIGATION PLAN	Doc No.: CL-CIP-201 Rev: REV.3 / 09June2021 Pg. 28 of 92
--	--	--

**Intensified treatment regimen (for HDRS non-responder subjects):** 5-7 days a week (intensity level - up to 60) 60±20 minutes per day (preferably in two equal sessions of 30±10 minutes each).

The treatment regimen assignment will be re-evaluated according to the subject HDRS score at visit 5 (after 4 weeks of open label treatment).

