### **9.1.5. Visit 4 – end of the DB phase (Day 56±7)**

Written below are the assessments to be completed at Visit 4 (either on site or remotely):

[figure not shown]
- Depression symptoms questionnaires:
  - By site qualified rater: HDRS21 (HDRS17- removing 4 last questions from the HDRS21), MDRS, CGI-S & CGI-I
  - By subject: QIDS-SR-16, Q-LES-Q. Subject self-reported questionnaire may be filled in electronically (ePRO) or by hard copy.
- Suicidal intent assessment by the investigator team (C-SSRS)
- Change in concomitant medications, if any.
- Significant change in health status, if any.
- Adverse events will be documented.
  - The characteristics of each subject study treatments regimen will be indicated on the subject binder.
  - At the end of the double-blind treatment phase treatment compliance would be verified as follows:
    - A stimulation session marked as “Pass” if a minimal average intensity of 25 on the Relivion®DP app (i.e= Minimal average stimulation of 2.57mA Trigeminal, and 6.92mA Occipital of the active stimulation), was delivered.
    - The first treatment week (Ramp Up) will not be counted for treatment compliance.
    - Expected treatment time for total DB phase: A total of 2400 minutes of “pass” treatment time (calculated as a scenario of 80 min per day, 5 days a week for 6 weeks).
    - Minimal patient compliance for the DB treatment period will be regarded as 70% compliance to the above cumulative “pass” stimulation time recommendation.
- DB treatment regimen compliant subjects will be offered to continue to the open label extension phase for additional 8±1 weeks.
- Treatment regimen non-compliant subjects will exit the study and return the device and iPhone, if provided. For these subjects this study visit would be the “end of study visit”.

- Once the OL treatment regimen allocation will be decided, the central trainer will contact the subject (on site or remote) to perform the device conversion to the open label mode (i.e. conversion of all devices to active mode), train the subjects on the assigned treatment regimen and re-train on the device use, if required.
- OL treatment regimens would include:
  - Maintenance treatment (for remitters): 40±10 minutes 3-4 times a week (intensity level up to 50)
  - Daily treatment (for responders): 5-7 days a week (intensity level up to 50) 60±20 minutes per day (preferably in two equal sessions of 30±10 minutes each).

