  - Daily Intensified treatment regimen (for non-responders): 5-7 days a week (intensity level up to 60) 60±20 minutes per day (preferably in two equal sessions of 30±10 minutes each).
- Study visit 4 may occur during a 4 days period to allow for the HDRS response, treatment compliance assessments and OL treatment allocation to be finalized and data to be provided to the central trainer who may schedule a remote training session with the subject. In any case, the subject would continue his/her previous treatment regimen up until the day of the device conversion to the open label mode. The device conversion day would be considered as the first day of the OL treatment phase.
- Subjects which completed the minimal stimulation time required by the protocol will be considered as DB phase completers.

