#### 9.1.6. Open label extension phase (Day 56±7- day 112±7)

- According to their visit 4 HDRS response assessment, subjects will be assigned into one of three open label treatment groups: Remitters/Responders/Non responders as follows:
  - Remitters: HDRS ≤7 at study visit 4 (week 8±1 post treatment initiation).
  - Responders: 50% ≥ HDRS score improvement from baseline at study visit 4 (week 8±1 post treatment initiation).
  - Non-responders: all other subjects who are not remitters or responders (50% <HDRS score improvement from baseline) at study visit 4 (week 8±1 post treatment initiation).

See Figure 5: Open label phase study flow.

 Neurolief Brain Innovation	MOOD: CLINICAL INVESTIGATION PLAN	Doc No.: CL-CIP-201 Rev: REV.3 / 09June2021 Pg. 50 of 92
--	--	--

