11.5.7 Additional Exploratory Endpoints and Analyses - Open Label Stage

1. The following endpoints will only be evaluated in the Relivion®DP treatment group for the mITT analysis set:

- Change from Baseline to 16 weeks post Relivion®DP treatment initiation in HDRS-17 (Visit 6).

The change from baseline HDRS-17 score will be modeled with a repeated measures ANCOVA model. The change will be modeled as a function of visit (categorical) with baseline value entered as a covariate. LSmean changes in HDRS-17 scores will be estimated from the model per visit and for the difference between visits and will be presented with 95% confidence intervals as well as level of significance (testing the null hypothesis

LSmean=0). The change from baseline in HDRS-17 score at visit 6 will also be compared to the change at visit 4.

- **Proportion of HDRS-17 responder subjects to visit 6.** The percent of subjects achieving at least 50% reduction from baseline in HDRS-17 total score to each visit in the original active group will be summarized by a count and percentage and compared between the visits using a GEE model (repeated measures model for binary data) programmed in the SAS GENMOD Procedure which will account for the within subject correlation, baseline HDRS-17 score will be entered as a covariate.

- **Proportion of subjects achieving clinically substantial improvement in HDRS-17 scores to visit 6,** defined as the percent of subjects with reduction in HDRS-17 score of at least 7 points at 16 weeks post Relivion®DP treatment initiation.

The percent of subjects achieving clinically substantial improvement in HDRS-17 scores at each visit in the original active group will be summarized by a count and percentage and compared between the visits using a GEE model (repeated measures model for binary data) programmed in the SAS GENMOD Procedure which will account for the within subject correlation, baseline HDRS-17 score will be entered as a covariate.

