- **SIQ (Satisfaction Questionnaire) Question #2:** Proportion of subjects rating the subjects convenience (score of 1, 2 and 3) to undergo a depression treatment that required a daily treatment (5-7 days a week) or maintenance treatment, defined as Very convenient, Somewhat convenient or Neutral, neither convenient nor inconvenient using a simple Likert-type scale whereas 1 = Very convenient, 2 = Somewhat convenient, 3 = Neutral, neither convenient nor inconvenient, 4 = Somewhat inconvenient, 5 = Very inconvenient, will be summarized by a count and

percentage and will be presented with two-sided exact 95% confidence interval.

- **SIQ (Satisfaction Questionnaire) Question #3:** Proportion of subjects rating the subjects convenience (score of 1, 2 and 3) to undergo a home based self-operated depression treatment, defined as Very convenient, Somewhat convenient or Neutral, neither convenient nor inconvenient using a simple Likert-type scale whereas 1 = Very convenient, 2 = Somewhat convenient, 3 = Neutral, neither convenient nor inconvenient, 4 = Somewhat inconvenient, 5 = Very inconvenient, will be summarized by a count and percentage and will be presented with two-sided exact 95% confidence interval.
- **SIQ (Satisfaction Questionnaire) Question #6:** Proportion of subjects rating the subjects ease (score of 1, 2 and 3) to administer the Relivion®DP treatment, defined as Very easy, easy , Neutral, using a simple Likert-type scale whereas 1 = Very easy, 2 = Easy, 3 = Neutral, 4 = Challenging, 5 = Difficult, will be summarized by a count and percentage and will be presented with two-sided exact 95% confidence interval.
- **SIQ (Satisfaction Questionnaire) Question #11:** Proportion of subjects satisfied from the study device effect on their depression status (score of 1 and 2), defined as Very satisfied and Satisfied, using a simple Likert-type scale whereas 1 = Very satisfied, 2 = Satisfied, 3 = Unsure, 4 = Dissatisfied, 5 = Very dissatisfied, will be summarized by a count and percentage and will be presented with two-sided exact 95% confidence interval.

3. The following endpoint will be evaluated in all subjects who did not achieve remission in the double-blind phase for the mITT analysis set regardless of prior double-blind treatment:

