- **Change from visit 4 to 16 weeks post Relivion®DP treatment initiation in HDRS-17 (Visit 6).** The change from visit 4 HDRS-17 score will be modeled with an ANCOVA model with baseline value entered as a covariate. LSmean changes in HDRS-17 scores will be estimated from the model and will be

presented with 95% confidence intervals as well as level of significance (testing the null hypothesis LSmean=0).

STATISTICAL

Final Audit Report

2024-05-29

Created:	2024-05-29
By:	[name] ([contact])
Status:	Signed
Transaction ID:	CBJCHBCAABAACkzPbHHLGM-xTDT9BogVTL12s5EmyqHM

"STATISTICAL" History

-  Document created by [name] ([contact])
2024-05-29 - 11:16:33 AM GMT
-  Document emailed to [name] ([contact]) for signature
2024-05-29 - 11:16:39 AM GMT
-  Document emailed to [name] ([contact]) for signature
2024-05-29 - 11:16:39 AM GMT
-  Document emailed to [name] ([contact]) for signature
2024-05-29 - 11:16:39 AM GMT
-  Document emailed to [name] ([contact]) for signature
2024-05-29 - 11:16:39 AM GMT
-  Email viewed by [name] ([contact])
2024-05-29 - 11:17:44 AM GMT
-  Document e-signed by [name] ([contact])
Signature Date: 2024-05-29 - 11:18:49 AM GMT - Time Source: server
-  Email viewed by [name] ([contact])
2024-05-29 - 11:29:52 AM GMT
-  Document e-signed by [name] ([contact])
Signature Date: 2024-05-29 - 11:31:46 AM GMT - Time Source: server
-  Email viewed by [name] ([contact])
2024-05-29 - 12:16:36 PM GMT
-  Document e-signed by [name] ([contact])
Signature Date: 2024-05-29 - 12:21:54 PM GMT - Time Source: server

Adobe Acrobat Sign

 Email viewed by [name] ([contact])

2024-05-29 - 3:31:37 PM GMT

 Document e-signed by [name] ([contact])

Signature Date: 2024-05-29 - 3:32:12 PM GMT - Time Source: server

 Agreement completed.

2024-05-29 - 3:32:12 PM GMT

Adobe Acrobat Sign

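### The exploratory open-label analysis of Visit 4 to Visit 6 change pools former sham and former active non-remitters and tests the change against zero, so it cannot separate starting active treatment from continuing it

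*SAP*

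**What the plan says.** SAP 11.5.7 has three groups of open-label analyses.

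- **Item 1** covers the original active arm only: "The following endpoints will only be evaluated in the Relivion®DP treatment group for the mITT analysis set". It includes a comparison of the Visit 6 change with the Visit 4 change, and counts of new responders and new remitters among those not in remission at Visit 4.
- **Item 2** pools both arms for the satisfaction questionnaire.
- **Item 3** takes "all subjects who did not achieve remission in the double-blind phase for the mITT analysis set regardless of prior double-blind treatment". On the model it says: "The change from visit 4 HDRS-17 score will be modeled with an ANCOVA model with baseline value entered as a covariate". Results are to be "presented with 95% confidence intervals as well as level of significance (testing the null hypothesis LSmean=0"). There is no term for prior arm or open-label regimen, and no per-arm estimate.

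The remission cut is in Protocol 9.1.6: "Remitters: HDRS ≤7 at study visit 4 (week 8±1 post treatment initiation"). At the end of the double-blind phase the protocol calls for "conversion of all devices to active mode" (9.1.5), so there is no concurrent control. Regimen then depends on the Visit 4 HDRS result. Responders who are not remitters get a daily regimen, and non-responders the "Daily Intensified treatment regimen (for non-responders): 5-7 days a week (intensity level up to 60"). Protocol 6.3.2 adds: "The treatment regimen assignment will be re-evaluated according to the subject HDRS score at visit 5".

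The efficacy analyses in Protocol 12.9 stop at week 8, so SAP 11.5.7 is the only plan for open-label efficacy.

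**The concern.** Three features of item 3 combine.

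1. One LS mean averages two different exposures: the first 8 weeks of active stimulation and a second 8 weeks of it.
2. The score that decides entry is also the starting point of the change, so regression to the mean pushes the result towards improvement.
3. The change is tested against zero in a phase where everyone is knowingly on active treatment. Natural course, expectation and permitted reductions in antidepressant dose (Protocol 9.7) can also move the score.

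The trial is meant to support marketing applications. A small p-value from item 3 could be read as showing that non-remitters benefit from switching to, or staying on, the device, and the analysis cannot show either. The summary that would be new, HDRS change in former sham subjects once they go active, is not planned anywhere.

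**Working it through.** **The plan's own figures.** No sample size, power or expected effect is stated for item 3. The only related figure is the double-blind size in Protocol 12.4: difference 3.3, SD 6, two-sided 5%, 80% power. The normal approximation gives 2 × (1.960 + 0.842)² × 6² / 3.3² ≈ 51.9, so 52 per arm. The two-sample t-test gives 52.87, so 53, as stated.

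**Step 1: pooling.** With a 50:50 mix, pooled mean = (former sham change + former active change) / 2.

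- Former sham −3.3, former active 0: pooled −1.65
- Both −1.65: pooled −1.65
- Former sham 0, former active −3.3: pooled −1.65

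Three different situations give the same LS mean, so the pooled result identifies neither component.

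**Step 2: selection.** Suppose scores in the full population do not change between Visit 4 and Visit 6 (same mean and SD, correlation ρ). For subjects selected because Visit 4 exceeds 7,

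E[V6 − V4 | V4 > 7] = −SD × (1 − ρ) × φ(c) / (1 − Φ(c)), with c = (7.5 − Visit 4 mean) / SD.

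Inputs:
- From Protocol 12.4: an active-arm change of −8.4 (the 6-week feasibility result), a sham change of −8.4 + 3.3 = −5.1, and 53 per arm before selection.
- Assumed, not in the documents: baseline HDRS-17 mean 20 to 24, Visit 4 SD 6 to 7 (6 being also the design SD for change), and ρ 0.5 to 0.9.

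Worked case, baseline 20, SD 6, ρ 0.5:
- Former active: mean 11.6, c = −0.683, 75% selected, artefact −1.26
- Former sham: mean 14.9, c = −1.233, 89% selected, artefact −0.63
- Pooled: (0.75 × −1.26 + 0.89 × −0.63) / (0.75 + 0.89) ≈ −0.92

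The last column is the share of simulated trials (2,000 per setting, one-sample t-test) that declare improvement with no true open-label change. The nominal rate in that direction is 2.5%.

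| Baseline, SD, ρ | Former active | Former sham | Pooled | Declared improved |
|---|---|---|---|---|
| 20, 7, 0.5 | −1.63 | −0.93 | −1.25 | 39% |
| 20, 6, 0.5 | −1.26 | −0.63 | −0.92 | 33% |
| 22, 6, 0.7 | −0.51 | −0.22 | −0.36 | 11% |
| 24, 6, 0.9 | −0.11 | −0.04 | −0.07 | 5% |

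Across the whole grid the pooled artefact runs from −0.07 to −1.25 points, false improvement from about 5% to 39%, and the share of an arm selected from 72% to 97%. Taking one Visit 4 mean for everyone gives similar values: −0.96 at mean 13, SD 6, ρ 0.5, and −0.37 at mean 15, SD 6, ρ 0.7.

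**Step 3: the covariate.** In a one-group linear model, the LS mean at the average covariate value equals the raw mean change. This holds whether baseline means the Visit 2 or the Visit 4 score, so the adjustment leaves the selection effect in the estimate.

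**The case against.** The strongest case against is that item 3 is descriptive. It sits under an exploratory heading, outside the testing hierarchy of SAP 9.2, and nowhere claims to estimate a switching or continuing effect. That stands: no confirmatory error rate is affected.

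Four stronger readings are tempting, and the documents do not support them.

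- A reader might infer that the analysis picks out subjects doing badly at Visit 4. The cut is only non-remission, so mild scores and responders are included. Most subjects qualify (82% to 89% at means of 13 to 15 with SD 6), which keeps the artefact small to moderate. At ρ = 0.9 it nearly vanishes.
- A reader might infer that continuing treatment is never described separately. Item 1 does that for the original active arm, though without a control. Only the former sham summary is missing.
- A reader might infer that former sham against former active is a clean contrast that should carry the inference. It is not. Regimen follows the Visit 4 score and may change at Visit 5. Entry is limited to compliant subjects who choose to continue (Protocol 8.2, 9.1.5). Only former sham subjects meet an unfamiliar stimulation sensation (9.1.6), so expectation differs. Among non-remitters the selection artefact itself differs by arm.
- A reader might call the 16-week label for Visit 6 an error. It is correct as study time. It misleads only if read as time on active treatment.

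**Conclusion.** The point holds as an inexpensive improvement to an exploratory analysis. Pooling and the absence of a control are the main faults, and they follow from the text without any assumption. The pooled LS mean cannot distinguish starting from continuing active treatment.

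Selection adds a secondary bias towards improvement of about 0.1 to 1.25 points. That size depends on the assumed Visit 4 means, SDs and Visit 4 to Visit 6 correlation, and on normal scores with no dropout. The false-improvement rates come from a plain one-sample test, so they approximate the planned ANCOVA. Nothing here bears on the primary, secondary or tertiary results.

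**What to change.** In SAP 11.5.7 item 3:

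- Add prior double-blind arm to the model and report the Visit 4 to Visit 6 LS mean change with a 95% CI for each prior arm.
- Run this on all subjects entering the open-label phase, and show non-remitters as a descriptive subset.
- Drop the p-value against zero as evidence of a device effect, and label the analysis uncontrolled.
- If the between-arm difference is shown, give it with a 95% CI as exploratory only. Note that regimen is assigned by Visit 4 HDRS, entry is limited to compliant and willing subjects, and the phase is open-label.
- State that Visit 6 is about 8 weeks of active treatment for former sham subjects and about 16 for former active subjects.

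This needs SAP wording and one model term, on data already collected. The cost is precision: with each arm about half the pooled set and a similar SD, per-arm intervals are about √2 ≈ 1.4 times as wide.
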